Aim 2.4: Examine factors related to successful uptake and implementation of the intervention in schools. The public health impact of an internet intervention is diminished if uptake of the intervention is poor. To understand factors related to implementation in schools, we will train school personnel at the end of the project in delivery of the FCU-Online intervention. We will assess feasibility, usage, coach fidelity, and uptake through engagement data collected via the website. Data from teachers and school administrators will be collected to examine factors that promote implementation in schools and that further our understanding of how this intervention will be applied in a real-world setting.

C. Methods, Materials and Analysis

This project includes several phases of research that involve different groups of participants who are recruited and consented at different times and in different ways. We have included a chart to help orient the reader to the sequence and timing of these phases. More detail about the method for each of these phases of research appears below.

Phase	Timing	Research participants	Status
1. Formulate research procedures, recruit schools for participation, program website, develop survey and questionnaires	Current – Fall 2016	N/A	Completed
1a. Focus groups with school staff and parents	May/ June 2016	Staff N=16; recruited from the schools selected in Spring 2016. Parent N=16; recruited from community. Participation will last 45 min.	Completed
1b. Usability testing	Fall 2016	N=5; recruited from Prevention Science Institute staff.	Completed
2. Pilot Study	Fall 2016	N=12 families with middle school-aged youth recruited from community.	Completed

3. Main research study	Winter 2017-Winter 2019	N=300 families of participating youth. Recruited over two school years. Participation will last 12 months.	Completed for Cohort 1; On-going for Cohort 2
4. Focus groups with parents of young children to modify existing website	Winter 2019	N=16; recruited from community. Participation will last 90 min.	On-going
5. Implementation in schools	2019	N= 5-10 school personnel; recruited from the schools who participated in the main research study. Participation will require about 15 hours of time spread out over 6 months. N=50-60 parents of middle school youth; recruited from the schools who participated in the main research study. Participation will require about 2 hours of time, spread out over 6 months.	Not yet started; will begin in April 2019

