Parent focus groups will begin with questions about their perceptions about parenting and child behavior and perceived barriers to receiving family support. Parents will also be asked about positive and negative experiences with computer education systems and preferences for presentation format. We will then provide an overview of the FCU Online program, including the purpose of the website and its current structure. This will include coverage of the three main elements of the website: an appraisal (aka the FCU assessment), feedback, and "Things to Try", a series of parenting skills training units that include brief videos and animations, interactive elements, tracking tools, quick tips, and a library of relevant articles and resources. This overview will also highlight the use of text messaging and the role of Coach consultations. Select pages of the website will be presented, including a welcome page, the FCU assessment, the feedback page, and one or more of the skills training units (e.g., Encouragement and Praise; Using Incentives; Limit Setting; Open Communication). At various points, participants will be asked a series of questions designed to elicit opinions and set the occasion for group discussion (see attached discussion questions). At the end of the session, participants will be asked to describe their overall reaction to the various features of the current program. Candid opinions will be encouraged including what participants did not like as well as any features they thought were missing and should be added.

5. Implementation in schools (N=70). In the last year of the project, we will train school personnel (e.g., school counselors) to deliver the FCU-Online intervention in their respective schools. These school staff members will now take on the role of “coach” that was described in the main study. For this phase of the research study, these staff members (and their ability to use the website to serve their communities) are the focus of study rather than parents. We will assess feasibility, usage, coach fidelity, and uptake through engagement data collected via the website. We will also interview these staff members to examine factors that promote implementation in schools to further our understanding of how this intervention could be applied in a real-world setting.

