We will meet with principals at the schools participating in the main research study to gauge their interest in participating in this phase of the project and whether or not they have staff who regularly work with families and who have time to participate in the study. At most schools these staff members are likely to be the school counselors, but that may vary by school depending on school resources. After receiving principal approval, the appropriate staff members (n=5-10) would then be recruited directly via email to participate in the project.

Once they consent to participate, these “coaches” would be trained by a member of the research team to use the website designed for coaches/ school personnel. This training will take about 6 hours and will cover both the technical skills needed to use the website as well as training in ways to use the information provided by parents to facilitate conversations about parenting and student behavior. Coaches would then each identify 5-10 families (total parent N= 50-60) at their respective schools that they think could benefit from the intervention. To participate in the study, parents will need to speak and read English and have computer access so that they can access the website, and not have participated in the main research study. To make it easier to identify families who have not already participated in the main research study, coaches will be asked to only recruit 6th grade families (because families who already participated now have 7th and 8th grade students). All families who participate in the implementation study would be assigned to the **web/mobile + coach condition** described previously because we are mainly interested in assessing how school personnel function in the coach role.

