Because the focus of the implementation study is school staff rather than parents, we will not be collecting baseline surveys or any of the follow-up surveys used in the main research study. Rather, parents will be identified by coaches, and enrolled directly in the website. After providing informed consent, parents will complete a qualtrics form that includes the information needed to enroll them in the website. The data provided via this form will be sent directly to research staff, who will use it to enter participants into the administrative website that triggers an email to participants thanking them for their willingness to participate and includes log-in information and directions for how to get started. Parents will complete the survey that is built into the website, receive computer generated feedback, and will then meet with their coach to discuss the feedback and the parenting modules presented on the website. The survey takes about 30 minutes to complete; parents may log-in and use the parenting resources as little or as often as they would like.

At the end of the study, parents will be asked to complete a 2-page Website Satisfaction Survey which will take about 10 minutes to complete. This survey will be administered via Qualtrics. An email with a link to the survey will be sent to parents approximately 6 months after they are enrolled in the study.

At the end of the study, coaches will be interviewed one-on-one by a member of the research team about the ways that they were able to use the website to work with families, any challenges that they encountered, and their insights into factors that could be improved to enhance implementation in schools. This interview will take approximately 1 hour.

Analysis

For our preliminary analyses, we will compare baseline characteristics of participants across conditions to test for significant differences; characteristics that differ across conditions will be used as covariates in subsequent analyses. Logistic regression analyses will be used to examine potential differences by study condition between dropouts and continuing participants on baseline measures. Attrition analyses will provide information about the external validity of the study, and interaction effects between condition and predictors will provide information about potential confounding effects (Cook & Campbell, 1979).

Aim 1: Design and evaluate a web-based FCU intervention that is guided by feedback from focus groups.

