regarding the potential moderating mechanisms, these analyses are considered exploratory. Each of the potential moderating effects (e.g., child sex, race/ethnicity, SES, baseline severity of child behavior, primary caretaker sex) will be investigated by conducting the above-mentioned mixed-effects analyses for each outcome that incorporate the Moderator × Condition interaction term. Significant moderating effects will be further probed to understand the nature of the conditional relation, using computational tools recommended by Preacher et al. (2006; www.quantpsy.org). Treatment acceptability will be demonstrated by achievement of the following benchmarks: (a) high level of program usage (e.g., 80% of targeted parents completing the FCU assessment and feedback sessions), and (b) high degree of consumer satisfaction (e.g., mean ratings > 4 on a 5-point rating scale on the Website Feedback Survey). We will also examine whether baseline participant characteristics (e.g., child sex, ethnicity/race, SES, severity of child behavior) are associated with treatment acceptability, program usage, and program usability.

Aim 2.4: Uptake and usage assessment of FCU-Online implementation. Uptake and receptiveness of the intervention by participating schools will be evaluated based on the FCU-Online program use data and the FAM-SET implementation assessment. We will use benchmarks to evaluate uptake and receptiveness similar to those described in Aim 2.3. We will compare program use metrics and FAM-SET scores between the controlled efficacy trial and the open trial using descriptive statistics. The qualitative feedback from the FAM-SET will be used to identify themes related to the barriers and facilitators of successful uptake, implementation, and sustainability.

D. Research Population & Recruitment Methods

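### In the school implementation phase, family uptake is to be read from website data that begin only at enrolment, no count of refusals is planned, and the benchmark's denominator is undefined

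*Protocol*

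**What the plan says.** Protocol section B, Aim 2.4, gives the reason for the phase: "The public health impact of an internet intervention is diminished if uptake of the intervention is poor".

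Section C.5 (Implementation in schools) names the measure: "We will assess feasibility, usage, coach fidelity, and uptake through engagement data collected via the website". The Analysis section, under Aim 2.4, bases school uptake on "FCU-Online program use data and the FAM-SET implementation assessment" and adds: "We will use benchmarks to evaluate uptake and receptiveness similar to those described in Aim 2.3". The Aim 2.3 usage benchmark, introduced there as an example, is "80% of targeted parents completing the FCU assessment and feedback sessions". Neither section says who counts as targeted.

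On how families enter, section C.5 says: "Coaches would then each identify 5-10 families (total parent N= 50-60) at their respective schools that they think could benefit from the intervention". Section D (Implementation study) and section E add that the coach gives the consent form to parents who seem interested. Section C.5 then says: "After providing informed consent, parents will complete a qualtrics form that includes the information needed to enroll them in the website". Research staff use that form to create the account.

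Other sources are planned. Coaches are interviewed at the end about how they used the site and what was difficult (C.5). Data from teachers and administrators are foreseen (Aim 2.4). FAM-SET comments are to be sorted into themes on barriers and facilitators (Analysis, Aim 2.4).

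The SAP reports the randomized comparison only and does not take up Aim 2.4.

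**The concern.** Between a coach thinking of a family and that family appearing in the website data there are four filters: selection by the coach, expressed interest, consent, and a submitted enrolment form. A family lost at any of these has no parent account. Nothing in sections C.5, D or E asks anyone to count such families.

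What the website can show about parents is therefore usage among those who accepted. Whether families take up the offer when a school counselor makes it is a separate question, and it is the one that Aim 2.4 ties to public health impact. A high completion figure among enrolled parents could be reported as good uptake when a substantial share of families declined, and the report would hold no number to correct that impression. Such counts are easy to keep at the time and hard to reconstruct afterwards.

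**Working it through.** **Inputs**
- School staff acting as coaches: 5-10 (C.5 and D).
- Families per coach: 5-10; parents in total: 50-60 (C.5 and D).
- Stated size of the phase: 70 (C.5).
- Example benchmark: 80% (Analysis, Aim 2.3).
- Share of identified families who do not enrol, r: not given in the documents, so it is an assumption here.

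**The plan's own figure.** The upper limits give 10 staff + 60 parents = 70, which reproduces the stated total. The lower limits give 5 + 50 = 55. The 80% has no derivation to reproduce.

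**How many families can be identified.** Coaches × families runs from 5 × 5 = 25 to 10 × 10 = 100. The text attaches the total of 50-60 to the families coaches identify, while the phase table in section C lists 50-60 as participating parents. The plan thus treats identified and enrolled as the same number. They coincide only if nobody declines.

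**Reading 1: *targeted* means enrolled.** Take 55 enrolled, the midpoint of 50-60. Completers needed: 0.80 × 55 = 44. This number does not depend on r, so the result is 80% whatever the refusals.

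**Reading 2: *targeted* means identified.** If completion among enrolled parents is 80%, completion among identified families is 0.80 × (1 − r).

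| Identified | Enrolled | r | Completers | Of enrolled | Of identified |
|---|---|---|---|---|---|
| 55 | 55 | 0% | 44 | 80% | 44/55 = 80% |
| 70 (assumed) | 55 | 15/70 = 21% | 44 | 80% | 44/70 = 63% |
| 100 (ceiling) | 55 | 45/100 = 45% | 44 | 80% | 44/100 = 44% |

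The 70 in the second row is an assumed number of identified families and is unrelated to the stated phase total of 70.

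**What the choice of denominator does to the threshold.** To reach 80% of identified families, completion among enrolled parents must be 0.80/(1 − r). That equals 100% at r = 20%, so above 20% the threshold is out of reach even if every enrolled parent completes. In counts, it tolerates at most 50 − 40 = 10 non-enrolling families of 50, 60 − 48 = 12 of 60, or 100 − 80 = 20 of 100.

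**Can the planned data support each reading?** Reading 1: yes, but the figure is insensitive to refusal. Reading 2: no, because families who do not enrol have no parent account and no other planned source is described as counting them.

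**The case against.** The strongest reply is that the plan does not rest uptake on website data alone and does not say that the benchmark is taken over enrolled parents. Much of this stands.

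- **The denominator.** A reader might infer that the 80% can be met however many families refuse. The documents do not support that as a flat statement. *Targeted* is undefined and may mean identified families, in which case each refusal counts against the benchmark. The 80% is itself only an example, carried over as a similar benchmark.
- **Other sources.** It would also go too far to say that poor uptake cannot be detected. The FAM-SET, the coach interviews and data from teachers and administrators can bring barriers to light. Themes about barriers do not give a proportion, however.
- **Replacement of refusers.** A reader might suppose that coaches go on offering until 50-60 parents are enrolled. No text describes replacement, and the 5-10 families per coach cap the identified families at 100. Scenarios beyond 100 lie outside the plan.
- **Staff and schools.** The same gap should not be read into these levels. The research team itself meets the principals and emails the staff, so it can count who agreed among those it approached. The plan merely does not say that it will report this.
- **Contact before consent.** Some families become known to research staff earlier, since parents with questions are referred to the project coordinator. No tally is planned there either.
- **Focus on staff.** Staff are the stated subject of this phase and have their own website, so engagement data may not be confined to parents. But their subject is how well they can serve families with the tool, and the share of families who accept bears directly on that.
- **Scale.** The phase is small, open and descriptive, which limits the weight of the point without removing it.

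**Conclusion.** The concern holds at family level. Parent engagement data exist only after selection, interest, consent and enrolment; no count of families who fall away is planned; and the benchmark's denominator is undefined. On one reading the benchmark ignores refusals, and on the other the planned data cannot supply its denominator, so both readings call for the same added count.

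Within the plan's limits, a result of 80% among 55 enrolled parents could correspond to 63% of 70 identified families or 44% of 100. These figures assume the stated numbers identified and 44 completers; the true refusal rate is unknown and could be zero, in which case the two denominators agree. The consequence is confined to the uptake claim under Aim 2.4. The comparison of the three randomized conditions is untouched.

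**What to change.** In sections C.5 and D:

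1. Have each coach keep an anonymous tally of families identified, offered the program, declined (separating refusal of the program from refusal of the research where known) and not submitting the form. Set it beside the counts enrolled and completing assessment and feedback.
2. Define *targeted parents* as families identified and offered the program by coaches.
3. Report completion of assessment and feedback on both denominators: families offered, called uptake, and parents enrolled, called usage.
4. Report schools and staff approached against those agreeing, from the research team's own contacts.
5. Do not transfer the 80% threshold to the offered denominator without justification. Nothing in the documents supports that level there, and it becomes unreachable once more than 20% of the families offered do not enrol.

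The cost is a short tick sheet without identifiers for 5-10 coaches and one definition. The reported uptake may look less favourable. The phase table in section C shows that this phase had not begun at the March 2019 version, so the tally could start with the first family. If the phase has since run without one, the parent figure should be labelled as completion among enrolled parents and not as uptake.

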Aim 2: Examine the efficacy of the FCU-Online intervention by conducting a randomized, controlled trial of 300 at-risk middle school youths. Research suggests that a live coach enhances outcomes associated with web-based interventions; however, a web-based intervention that requires no coaching can be widely disseminated and has greater potential for a large public health impact. We will examine outcomes associated with a web/ mobile + coach version and a web/ mobile-only version of the FCU. Families will be randomly assigned to the FCU-Online intervention (100 web/ mobile+coach, 100 web/mobile-only) or a waitlist control group that receives middle school as usual for 12 months and then access to the web/mobile only condition (n=100).

Version 3.18.19

Aim 2.1: Evaluate main effects of both versions of the FCU-Online, including academic achievement, behavioral control, family cohesiveness, and delayed onset of substance use.

Aim 2.2: Test a developmental, mediational model in which parenting skills and behavior mediate changes in youth behavior over time. It is expected that families who receive the FCU will show reductions in growth of youths' risk behavior, compared with the waitlist control group. Reductions will be mediated by positive changes in parenting behaviors and parenting skill development.

Aim 2.3: Examine moderators, including gender, ethnicity, and socioeconomic status, and model intervention effects by testing moderators over time. We will assess the feasibility of the FCU as an internet-delivered intervention in middle schools, the extent to which participants engaged in the intervention and complete the program, satisfaction with the program, and effects of the FCU on improved parenting skills, positive youth adjustment, and reductions in youth problem behavior over two years.

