We will recruit and randomly assign 300 families with middle school youths (6th and 7th grade) to one of three conditions: (a) web/mobile + coach intervention (n=100), (b) web/ mobile-only intervention (n=100), or (c) waitlist control group (n=100) that will receive middle school as usual and then offered the web/mobile-only intervention immediately after completing their final time point of data collection (12 months after enrollment). This design will enable us to compare outcomes associated with the web/ mobile-only intervention with a coach version. Participants will be randomly assigned to condition within school such that each school will have a similar number of participants in each of the three conditions. Participation in this study will be 12 months for all families, regardless of condition.

Families in all three conditions will be mailed a packet that includes a parent consent form, youth assent form, the parent and youth surveys, and 4 self-addressed, stamped envelopes so that each consent and survey may be mailed back separately to project staff. This “pre-assessment” includes standard, widely-used questionnaires that ask questions about the child's abilities and behavior, parenting practices, family dynamics, family demographics, family health behaviors, and life stressors and take about 30 minutes to complete. At the time of the pre-assessment, parents will also be asked to provide research staff with their driver's license number. We collect these because they assist us in relocating families for subsequent phases

of this longitudinal research project if they were to become lost. Our research team subscribes to a service which allows us to search for individuals by DL numbers to obtain a new address or phone number from items such as utility bills. Driver's license numbers will be retained for the duration of the research project. Participants will be assured that this information will be kept private, consistent with other data collected, and will be destroyed no later than 5 years after the end of the project.

One week after mailing this packet, a paid staff member will call the caregiver to see if the caregiver or youth have any questions about the consent form or the survey. If the family has not yet returned their surveys, they will be reminded to do so as soon as possible.

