Aim 2.1: Analysis of main effects. The hypotheses tested in this aim are (a) families in each intervention condition will show significant improvements on the outcome variables, compared with youths in the control condition, and (b) families assigned to the web/mobile+ coach condition will have significantly better outcomes compared with those assigned to the web/mobile-only condition. The primary outcomes include academic competence, youth behavioral control, delayed onset of youth substance use, reduced family conflict, increased family cohesion, and positive family relationships. The secondary outcomes include the putative mediating mechanisms of parenting skills and behaviors. Families will be randomized to condition and will be the unit of analysis for all models. Mixed-effects analyses will be based on a hierarchical linear modeling approach in which students are nested within schools, primary outcomes are nested within individual students at Level 1 of the model, and between-subject predictors (fixed effects), such as treatment condition and child/parent demographics, will be examined at Level 2. For each of the three pairwise contrasts between conditions, intervention effects will be examined by modeling longitudinal trajectories across time with mixed-effects models using SAS PROC MIXED or mPlus software.

Aim 2.2: Mediation model testing. We will test whether change in the putative mediating mechanisms of parenting skills and behaviors (e.g., change from baseline to 3-month follow-up) mediate the association between study conditions and longitudinal trajectories of the youth and family outcomes.

Aim 2.3: Examine moderating effects and intervention process measures. The moderation analyses will follow recommendations by Kraemer and colleagues (2002) and analytic methods of Aiken and West (1991), Jaccard and Turrisi (2003), and Preacher et al. (2006). Because we do not have specific hypotheses

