have been previously reported (Stormshak et. al., 2019). Briefly, parents in the study were predominately female, on average 40.0 ($SD = 6.1$) years of age, and 35% had a 4-year college degree or graduate training. The children in the study were approximately gender balanced, mostly white, and mostly lived in suburban environments. Use of the site was robust, but the web plus coach group used the program significantly more than the web-only group. Participants in the three conditions did not differ on gender, area (rural, suburban, urban), minority status, SES risk score or pretest measures of the outcomes indicating randomization produced initially equivalent groups. The correlations of the pretest measures ranged from $r = -.67$ to $r = .60$ (mean $|r| = .30$).

The outcomes approximated normal distributions except conduct problems which was normalized with a logarithmic transformation. Complete data was available for 88% of the sample and attrition was 6% at posttest, 8% at 6-month follow-up and 9% at 1-year follow-up. Number of assessments completed was not significantly associated with study condition, child's gender and child's race (all p -values $> .08$). Comparison of linear and non-linear unconditional models showed a linear model had superior fit to a linear and quadtric model for all study outcomes.

Table 1 provides means and standard deviations for the outcomes at each assessment point for each of the three conditions. Table 2 provides a summary of the condition effects from the growth models for the three a priori comparisons and is a test of whether groups differed in change in outcomes from pretest to the 1-year follow-up. No statistically significant (at $p < .017$) differences were found, although one trend-level effect ($p < .10$) is worth noting. The web plus coach group showed trend level differences in sense of parenting importance that favored the

web plus coach group relative to the wait-list control group, a small to medium effect (p -value = .081, $d = .28$), a small to medium effect (Cohen, 1988).

	Pretest		3-Month Posttest		6-Month Follow-up		1-Year Follow-up	
	M	SD	M	SD	M	SD	M	SD
Wait-list control	1.05	1.38	1.24	1.54	1.00	1.44	1.08	1.45
Web-only intervention	1.37	1.81	1.32	1.63	1.17	1.57	1.19	1.40
Web plus coach intervention	1.44	1.65	1.30	1.55	1.12	1.54	1.21	1.60
Hyperactivity								
Wait-list control	3.45	2.69	3.31	3.43	3.24	2.32	3.46	2.56

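### Five of the protocol's six primary outcomes, including onset of substance use, are neither analysed nor explained in the SAP, which also ranks none of its outcomes

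*Protocol*

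**What the plan says.** Protocol section B, Aim 2.1, sets the efficacy question: "Evaluate main effects of both versions of the FCU-Online, including academic achievement, behavioral control, family cohesiveness, and delayed onset of substance use". Section C, Analysis, Aim 2.1, turns it into outcomes: "The primary outcomes include academic competence, youth behavioral control, delayed onset of youth substance use, reduced family conflict, increased family cohesion, and positive family relationships". Later in that paragraph parenting is placed in a lower class: "The secondary outcomes include the putative mediating mechanisms of parenting skills and behaviors". It plans longitudinal mixed-effects models for all three pairwise comparisons of the arms.

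The SAP, which already contains results, gives one growth-model specification and applies it to every outcome. Table 2 then reports effortful control, sense of parenting importance, sense of parenting confidence, parenting self-efficacy, conduct problems, hyperactivity and emotional problems. On the type of outcome it says: "The outcomes approximated normal distributions except conduct problems which was normalized with a logarithmic transformation". On the shape of change it says that model comparison "showed a linear model had superior fit to a linear and quadtric model for all study outcomes". No outcome is labelled primary or secondary; only the three contrasts are called a priori. The earlier report it cites is cited for sample description, program use, baseline equivalence and pretest correlations, not for any outcome result.

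**The concern.** The trial's title is about preventing substance use, and delayed onset is a declared primary outcome. After its own title, the SAP does not mention substance use again. If the SAP is followed as written, the trial supports no conclusion, positive or null, on substance use, academic competence, family conflict, family cohesion or family relationships.

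The lack of ranking makes this hard to see. The SAP reports that nothing reached its threshold, which reads as a null for the program as a whole, although it covers at most one primary. The single effect it draws attention to is on sense of parenting importance, a scale that appears to belong to the protocol's secondary domain. The documents do not show when or why the outcomes analysed came to differ from those declared. Because the SAP was issued with results, selection after seeing data can be neither shown nor excluded.

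**Working it through.** **The plan's own threshold.** The SAP uses p < .017. A Bonferroni split over three contrasts gives .05/3 = .0167, which rounds to .017. The SAP does not state this derivation.

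**Matching outcomes.** Protocol primaries (Analysis, Aim 2.1) against the rows of SAP Table 2:

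| Protocol primary | Table 2 outcome |
|---|---|
| Academic competence | none |
| Youth behavioral control | effortful control; arguably conduct problems and hyperactivity |
| Onset of substance use | none |
| Family conflict | none |
| Family cohesion | none |
| Positive family relationships | none |

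The three parenting scales and emotional problems match no primary.

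**Counts.**
- Planned: 6 primaries × 3 contrasts = 18 tests. Covered, counting one test per primary and contrast: 1 × 3 = 3. Absent: 18 − 3 = 15, and 15/18 = 83%.
- Table 2 has 7 × 3 = 21 rows. Effortful control takes 3 (14%). Adding conduct problems and hyperactivity makes 9 (43%), with p-values from .142 to .854. Parenting scales take 9 (43%) and emotional problems 3 (14%).
- The highlighted trend: .081/.017 = 4.8 times the threshold.

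**Could lost table rows explain it?** Table 1 is damaged in the text available and proves nothing. Table 2 lists the same seven outcomes in all three contrast blocks, so a loss would have had to remove the same rows three times. The SAP's statements on normality and linear change also leave no place for an event that happens once.

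**What an onset analysis could deliver.** The documents give no incidence, so 5%, 10% and 20% at 12 months are assumptions. The number per arm is 100 (protocol) less 9% attrition at one year (SAP) = 91, before removing youths who already report use at pretest. The half-width of the 95% interval for a risk difference is 1.96 × √(2p(1−p)/91). Power is for a two-proportion test with pooled variance, two-sided at .017, comparing p with p/2.

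| Assumed incidence p | Events per arm (91p) | Half-width | Power to detect a halving |
|---|---|---|---|
| .05 | about 5 | .063 | .07 |
| .10 | about 9 | .087 | .13 |
| .20 | about 18 | .116 | .31 |

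**The case against.** The strongest reply is that this SAP may cover only a subset of outcomes. It opens at data analysis, has no measures section and sends baseline findings to an earlier report. The documents therefore show an omission, not a decision to change outcomes. That is fair as to motive and timing, which are unknown. But the SAP points to no other analysis of the missing primaries, and saying so would itself be part of the repair.

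Second, the 83% depends on the count. Section B names four outcomes, "academic achievement, behavioral control, family cohesiveness, and delayed onset of substance use"; on that list 3 of 4 (75%) are missing. By exact name, none of the six primaries appears in Table 2 (100% missing). The figure is one reading within 75% to 100%, and every reading leaves most of the efficacy question untested.

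Third, neither document maps scales to constructs, and importance, confidence and self-efficacy could be read as beliefs rather than skills or behaviors. So the sponsor should state the mapping. The scales still match none of the six primaries, so ranking them below primary follows the protocol.

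Fourth, the protocol describes the survey content only in general terms, including "parenting practices, family dynamics, family demographics, family health behaviors, and life stressors", and defines no onset variable. Onset may not have been measured, and an event model would be a new specification. Both points stand. They limit which analyses can be added, but they do not excuse silence about a declared primary.

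Finally, the SAP calls the p = .081 result a trend and claims no efficacy from it. That is correct. The result matters here only because nothing tells the reader which class of outcome it belongs to.

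**Conclusion.** The concern holds, and the SAP has to be corrected. Five of six declared primaries (15 of 18 tests, 83%) have no analysis and no explanation, and no outcome is ranked. Five is the lenient count, since it credits behavioral control through effortful control and possibly conduct problems and hyperactivity, a mapping the documents never state. The overall null therefore applies to at most one primary. That the highlighted trend lies on a secondary is probable rather than certain. The conclusion does not depend on the onset precision figures, which rest on assumed incidences and on the planned arm size, because the SAP gives no arm sizes.

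**What to change.** Amend the SAP as follows.

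- List the six protocol primaries, each with the scale used to measure it.
- Run the same three contrasts on every primary that was collected. For any not collected or not analysed, state why and when it was dropped, or where it is reported.
- Label the parenting scales secondary. Label any outcome that maps to no primary, such as emotional problems, secondary or exploratory.
- For substance use, use a model suited to a once-only event. One example is a discrete-time hazard or binary model of first use by 3, 6 and 12 months among youths reporting no use at pretest, with cumulative incidence by arm.
- Limit the efficacy conclusion to the outcomes actually tested.

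The mapping, explanations, ranks and narrower conclusion need no new data. The added analyses come to at most 15 tests and apply only to measures that were collected. They were not specified before results were available and should be described that way. Under the assumptions above, power to detect a halving of onset is only 7% to 31%, so onset should be reported mainly as an estimate with its interval (about ±6 to ±12 percentage points).
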